### DESIGN:

This Phase II, randomized, 3-arm, placebo controlled, partially blinded, clinical trial will be conducted in 990 healthy, HIV-uninfected, QFT-GIT negative, previously BCG vaccinated adolescents. The trial will be conducted at the South African Tuberculosis Vaccine Initiative (SATVI) site in the Worcester region of the Western Cape region of South Africa, where

epidemiological studies involving thousands of adolescents have been conducted over the last decade to characterize rates of *Mtb* infection and active TB disease in this age group. Additional sites with similar TB epidemiology may also be used.

Subjects will be enrolled in two sequential cohorts and within each cohort subjects will be randomized in a 1:1:1 ratio to receive either AERAS-404 or saline placebo on Days 0 and 56, or BCG Vaccine SSI on Day 0. The first 90 subjects (30 from each arm) will form the Safety & Immunogenicity Cohort and will be subject to more intensive collection of safety data, with data reviewed by the Data Monitoring Committee (DMC), principal investigator and local medical monitor. Selected immunogenicity assays, including whole blood intracellular cytokine staining (ICS), will also be performed in this cohort. The remaining 900 subjects will be enrolled into the Correlates Cohort. All 990 subjects in the study will be evaluated for safety and biomarker outcomes, and for prevention of *Mtb* infection.

The primary *Mtb* infection endpoint will be QFT-GIT conversion from a negative to positive test, using the manufacturer's recommended threshold of 0.35 IU/mL, at any time-point after Day 84 and through end of follow-up for the primary endpoint (see Figure 2-1). The 84-day 'wash-out' period is stipulated in order to exclude subjects who may have already been *Mtb* infected, but not yet converted their QFT-GIT test at screening, thus subjects who convert their QFT-GIT at Day 84 will not be included in the analyses of prevention of *Mtb* infection.

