## 1.1 Background

The high incidence of *Mtb* infection and active TB disease among adolescents in high TB burden countries suggests that trials assessing vaccine-induced protection are critical in this age group. Approximately 50% of high school students in the Worcester region, near Cape Town, South Africa, test QuantiFERON®-TB Gold in-tube (QFT-GIT) positive (Mahomed et al, 2011a). The incidence of active TB disease in this same adolescent study population is similarly high (450 per 100,000 person years) (Mahomed et al, 2013). Further, the increase in active TB disease incidence that begins in adolescence occurs in parallel with a very high incidence of QFT-GIT conversion, with QFT-GIT conversion rates (the denominator being QFT-GIT negative individuals) increasing by 14% to 17% per year between 13-17 years of age (*unpublished SATVI data*).

Adolescents who are QFT-GIT positive have an almost three-fold higher incidence of active TB disease in subsequent years, compared to QFT-GIT negative adolescents (640 vs 220 per 100,000 person years) (Mahomed et al, 2011b). However, the highest risk of TB disease occurs in adolescents with recent QFT-GIT conversion. Adolescents who were known to have converted from QFT-GIT negative to QFT-GIT positive over a preceding two-year period had eight-fold higher TB disease incidence in subsequent years, compared to adolescents who had remained QFT-GIT negative (1,460 vs 170 per 100,000 person years) (Machingaidze et al, 2012). Therefore, QFT-GIT conversion has clear biological importance as a risk factor for active TB disease in this age group. It follows that demonstration of prevention of QFT-GIT conversion would be a critical step towards control of TB disease incidence among young adults. This clinical trial will test whether vaccination with AERAS-404 or BCG revaccination prevents QFT-GIT conversion among healthy, HIV-uninfected, QFT-GIT negative, previously BCG vaccinated adolescents.

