**Figure 2-1 Schematic of Follow Up and QFT-GIT Testing**

Based on previous data from baseline QFT-GIT negative adolescents at the SATVI site, we expect the incidence of active TB disease in the study population to approximate 0.2% (estimate 2 cases per year of follow-up) (Mahomed et al, 2011b). While the total number of active TB disease cases is expected to be very low and the study is not powered to detect a difference in rates of active TB disease among the vaccine groups, data on the number and type of cases of active TB disease (as defined in Section 3.6.1) will be captured as part of the assessment of safety.

Immunological outcomes will include intracellular cytokine staining (ICS) on PBMCs and whole blood, transcriptomics on RNA from whole blood, absolute blood cell subset counting by flow cytometry (for deconvolution of transcriptomics), quantification of soluble immune mediators by multiplex ELISA (all in the Safety & Immunogenicity Cohort only), and exploratory assays using PBMCs, plasma, RNA, and absolute blood cell subset counting samples for correlates of risk/protection analyses in all subjects.

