### 3.6 Study Evaluations

The 90 subjects enrolled in the Safety & Immunogenicity Cohort will have more intensive evaluation of safety and immunologic data. The remaining 900 subjects will be enrolled into the Correlates Cohort. All 990 subjects in the study will be evaluated for safety and biomarker outcomes, and for prevention of *Mtb* infection.

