### 14.3.2. ANALYSIS OF EXPLORATORY EFFICACY ENDPOINT

The following tables will be presented for the Modified Intent-to-treat analysis set:

- QuantiFERON levels (IU/mL) upon and following first positive QFT-GIT result:
  - o Default summary statistics for QFT-GIT results at the following time points:
    - First positive QFT-GIT result:
      - The p-value based on the Mann-Whitney-Wilcoxon test will be used for pair-wise comparisons between treatment groups.
    - 3 months-post first positive QFT-GIT result:
      - Number and percentage (%) of participants with a negative QFT-GIT.
    - 6 months-post first positive QFT-GIT result:
      - Number and percentage (%) of participants with a negative QFT-GIT.
  - o This table is to include all participants with at least one positive post-Day 84 QFT-GIT result.
  - o This table will be repeated for the Per Protocol analysis set.
- First QuantiFERON reversion:
  - o Number of participants with first QFT-GIT negative value within the following categories will be included:
    - Within 3 months post-conversion.
    - Within 6 months post-conversion.
    - At any time during follow-up.
  - o At risk defined as participants with:
    - A primary endpoint.
    - A QFT-GIT result available at the relevant visit within 6 months (for the first two lines) or at any time post-initial conversion (for the third line) after the primary endpoint occurrence.
  - o This table will be repeated for the Per Protocol analysis set.
- Alternative QFT-GIT thresholds:
  - o Number and percentage of participants who EVER experienced the following alternative threshold values (i.e., at any post-Day 84 timepoint):
    - $\geq 0.20$ .
    - $< 0.2$  at any time point prior to conversion and  $> 0.70$  at any time point post-Day 84.
    - $> 0.70$ .
    - $> 4.0$ .
  - o Vaccine efficacy presented:
    - Point estimate (based on the conditional binomial distribution).
    - 95% CI (based on the conditional binomial Clopper-Pearson method with mid-p correction).
  - o This table will be repeated for the Per Protocol analysis set.
- Trends in QFT-GIT sustained conversions and end-of-study reversions:
  - o Number and percentage (%) of participants in each category:
    - Participants who were negative at Month 24 or the Month 24 call-back visit. Percentages (%) will be calculated based on the number of participants with non-missing Month 24 or Month 24 call-back values.

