    - o This table will be repeated for the Per Protocol analysis set.
  - Participants who converted, reverted, and time to conversion among reverters and non-reverters:
    - o Number and percentage (%) of participants who:
      - Converted.
      - Converted and later reverted.
      - Converted and did not revert.
    - o The median time and the quartile 1 (Q1) and 3 (Q3) values will be displayed for:
      - Time to conversion among all converters.
      - Time to conversion among all reverters.
      - Time to conversion among non-reverters.
    - o This table will be repeated for the Per Protocol analysis set.
  - QFT-GIT positivity patterns over time from initial conversion timepoint onwards:
    - o Number and percentage (%) of participants, summarized for the following patterns in the order specified below:
      - +/+/+/+
      - +/+/+
      - +/+m

Document: Aeras\_C-040-404\_SAP\_V2\_0

Author: [name]

Version Number:

2.0

Version Date:

29SEP2017

Template No: CS\_TP\_BS016 – Revision 3

Reference: CS\_WI\_BS005

Effective Date: 01May2012

Copyright © 2012 Quintiles Transnational Corp. All rights reserved.

The contents of this document are confidential and proprietary to Quintiles Transnational Corp. Unauthorized use, disclosure or reproduction is strictly prohibited.

- +/m/+
  - +/m/m/m
  - +/+/+/-
  - +/-/+/+
  - +/+/-/+
  - +/+/-
  - +/-/+
  - +/-/
  - +/-/
  - +/-/
  - +/-/
  - +/-/
  - +/-/
  - +/-/
  - +/-/
  - +/-/
  - +/-/
  - +/-/
  - +/-/
  - +/-/
  - This table will also be repeated for the Per Protocol analysis set.
- Clinical TB diagnosis:
    - o Number and percentage of participants in each of the following categories:
      - Participants who received at least one TB work-up:
        - Bacteriologically-confirmed TB.
        - Clinical TB (based on the Investigator's assessment).
    - o The total number of TB work-ups performed.
    - o This table will be repeated for the Per Protocol analysis set.

The following figures will be presented for the Modified Intent-to-treat analysis set:

- Quantitative QFT-GIT results following initial conversion:
  - o Box-and-whisker plots per treatment group for the following:
    - QFT-GIT result at 0, 3 and 6 months since first QFT-GIT conversion (reference line at 0.35 IU/mL to be included).
    - QFT-GIT Change from Baseline at 3 and 6 months since first QFT-GIT conversion (reference line at 0 IU/mL to be included).

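### The protocol treats active TB as safety data, but the SAP's only TB table is on the mITT and Per Protocol sets, which leave out Day 84 converters and anyone without a Day 84 result

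*SAP*

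**What the plan says.** **Protocol.** Section 2.2 expects active TB incidence to "approximate 0.2% (estimate 2 cases per year of follow-up"). It says the study is not powered to compare arms on TB, and that data on the number and type of cases "will be captured as part of the assessment of safety". Section 3.6 adds: "All 990 subjects in the study will be evaluated for safety and biomarker outcomes". The exclusion of Day 84 converters is tied to one purpose: "subjects who convert their QFT-GIT at Day 84 will not be included in the analyses of prevention of" Mtb infection (Study Abstract, Design; also section 2.2). Section 1.1 gives TB incidence in recent converters against persistent negatives as "1,460 vs 170 per 100,000 person years".

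**SAP.** Section 5.2 makes the Safety set, analysed as treated, the primary set for safety analyses, and section 16 repeats this for safety outputs. Section 16 contains no TB output. The Clinical TB diagnosis table is in section 14.3.2 under the line "The following tables will be presented for the Modified Intent-to-treat analysis set". It gives number and percentage for "Participants who received at least one TB work-up", split into bacteriologically confirmed and clinical TB, plus the number of work-ups. Then: "This table will be repeated for the Per Protocol analysis set". It states no denominator, start date or person-time. Section 5.3 defines mITT as the Safety set restricted to a negative Day 84 QFT-GIT, and section 5.5 makes Per Protocol a subset of mITT. Section 14.3.2 also plans a listing of TB diagnosis and assessment for the Randomized set. Section 3.3 takes the analysis of TB incidence trends out of this SAP. It does not mention that the TB summary has been placed on mITT.

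**The concern.** An outcome designated as safety is summarised by arm only in a population chosen for the infection endpoint. The selection rule is a post-vaccination test result, and it removes recent converters, whom the protocol identifies as the highest-risk group for TB.

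Other Safety-set tables do not fully cover the gap. Unsolicited adverse events are tabulated only within the 28-day windows after each dose (SAP 16.1.9), and TB is not on the list of adverse events of special interest (SAP Appendix 4). A TB case judged non-serious, starting outside those windows in a Day 84 converter, would appear in the listing but in no table. With about four cases expected over three arms, one such case matters to the by-arm description.

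**Working it through.** **1. The protocol's own figure.** 990 × 0.002 = 1.98 cases per year, which reproduces the stated 2. The risk ratio for recent converters is 1,460 / 170 = 8.6.

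**2. Day 84 converters left out.** Annual conversion is 10% for planning and 17% as the observed local average (protocol 7.6). Reading these as annual risks and assuming no vaccine effect by Day 84:
- 10%: 990 × (1 − 0.90^(84/365.25)) = 23.7
- 17%: 990 × (1 − 0.83^(84/365.25)) = 41.5

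That is about 24–42. Read as constant hazards, the same rates give 23–38.

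**3. Expected TB in those converters during scheduled follow-up.** The last visit is Day 168 for BCG and Day 224 for AERAS-404 and placebo (protocol Tables 3-1 and 3-2), which is 84 and 140 days after Day 84. Mean follow-up is (84 × 1/3 + 140 × 2/3) / 365.25 = 0.332 years. At 1.46% per year:
- 23.7 × 0.332 × 0.0146 = 0.11
- 41.5 × 0.332 × 0.0146 = 0.20

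**4. Early TB (Days 0–84), all participants.** 990 × 84/365.25 = 227.7 person-years. At 0.17% per year this is 0.39 cases, and at 0.20% it is 0.46. Only early cases with a positive or missing Day 84 test leave the table. The documents do not say what fraction that is, so counting all of them is a ceiling.

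**5. Missing Day 84 results.** At 7% per year loss (protocol 7.6), 990 × (1 − exp(−0.07 × 84/365.25)) = 15.8 participants are gone by Day 84. They add no observed TB after they leave. Some participants may miss the test but stay in the study. The documents give no number for them; every ten would add about 10 × 588/365.25 × 0.002 = 0.03 cases to Day 672.

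**6. Ceiling outside the table against cases inside.**
- Outside: 0.39 + 0.11 = 0.50 to 0.39 + 0.20 = 0.59. With 0.20% in step 4, the top becomes 0.46 + 0.20 = 0.66.
- Inside, after Day 84: about 3.1–4.1. Assumptions: 315 mITT participants per arm, both vaccines halving conversion, TB hazard 0.17% per year before and 1.46% after conversion, no further loss, and call-back attendance from none to complete.
- Total: 3.1 + 0.5 = 3.6 to 4.1 + 0.6 = 4.7, so roughly 4.

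Day 84 converters, the one group certain to be excluded, account for about 3–5% of the total (for example 0.11/3.6 and 0.20/(3.47 + 0.59), where 3.47 is the inside figure at 17% with no call-back).

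**7. Would person-time change the arm comparison?** Using the step 6 assumptions with no call-back, placebo against an arm with conversion halved:

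| Conversion | Person-years (placebo, vaccine) | Crude ratio | Rate ratio | Ratio if followed to Day 672 |
|---|---|---|---|---|
| 10% | 500.0, 503.6 | 0.887 | 0.881 | 0.83 |
| 17% | 494.5, 501.1 | 0.847 | 0.836 | 0.78 |

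Person-years differ by 0.7–1.3%, so dividing by them barely moves the ratio. The larger gap, between the crude ratio and the last column, comes from high-risk time that nobody observes. It closes if every Month 6 and Month 12 converter attends the call-back.

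**The case against.** The strongest reply is that nothing is hidden. Every TB case appears in a listing for the Randomized set, sorted by treatment group (SAP Appendix 1). TB judged serious, including as a medically important condition, enters Safety-set SAE tables with collection through database lock. Non-serious TB within 28 days of a dose enters the adverse event tables. The protocol promises that TB data will be captured as safety; it promises no rate table, and the SAP openly drops the TB trend analysis. All of this stands and keeps the point minor. It does not supply a by-arm count on the population the plan uses for safety.

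Three stronger readings are tempting, and the documents do not support them.

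- **The table omits the first 12 weeks.** It sets no start date, and mITT selects on the QFT-GIT result, not on TB. A participant with early TB and a negative Day 84 test is counted.
- **Shortened follow-up of converters biases the table.** Month 18 and Month 24 converters are followed to Months 24 and 30, no less than non-converters. Month 6 and Month 12 converters are asked back for a TB assessment at 24 months or later (protocol 2.2), although attendance needs separate consent. Day 84 converters do leave early, but they are not in this table.
- **Some 15–20% of cases are lost.** That treats every early case as having a positive or missing Day 84 test, which no passage supports.

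The reply is also right that moving to the Safety set has a cost: it brings in Day 84 converters, whose last scheduled visit differs by arm.

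**Conclusion.** The mismatch is real and minor. TB is designated as safety data, the Safety set is the stated basis for safety outputs, and the only TB table uses sets that exclude Day 84 converters and participants without a Day 84 result. The firm part is about 24–42 converters and 0.1–0.2 expected cases. The ceiling is about 0.5–0.6 of roughly 4 cases, or up to 0.66 if early TB runs at 0.20% per year. These sizes rest on the protocol's incidence figures, 10–17% annual conversion, no vaccine effect by Day 84, and participants without a Day 84 result having left the study. No inference is planned on this table, so the consequence is a possibly incomplete by-arm description, not an error in a test. Crude percentages are not a material defect here, and person-time cannot restore follow-up that was not observed.

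**What to change.** In SAP 14.3.2, or in section 16 as a safety output:

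1. Present the Clinical TB diagnosis table on the Safety analysis set, as treated, counting from Day 0.
2. State the denominator: all participants in the arm, or only those worked up.
3. Show Day 84 converters as a separate row with their follow-up time, because their last scheduled visit is Day 168 for BCG and Day 224 for AERAS-404 and placebo.
4. As descriptive context, add cases per person-year with an exact confidence interval by arm, and Month 24 call-back attendance by arm.
5. Keep the mITT and Per Protocol versions as supportive, and record the choice of set in section 3.3.

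The cost is SAP wording and one re-run table; the TB symptom screens and TB case report forms are already collected. The one downside is the unequal follow-up of Day 84 converters across arms, which item 3 makes visible.

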### 14.3.3. DERIVATIONS

Based on the aforementioned, the following variables, as presented in the planned TLF shells, will be derived for post-vaccination visits and/or time points:

- QFT-GIT result classification (refer to Section 14.1.3: Derivations). Substitute the primary analysis threshold value with the alternative threshold value.
- Available follow-up time (months) until QFT-GIT:
  - o Months represent the available follow-up time (months) per participant since first QFT-GIT conversion.

---

Document: Aeras\_C-040-404\_SAP\_V2\_0

Author: [name]

Version Number:

2.0

Version Date:

29SEP2017

Template No: CS\_TP\_BS016 – Revision 3

Reference: CS\_WI\_BS005

Effective Date: 01May2012

Copyright © 2012 Quintiles Transnational Corp. All rights reserved.

The contents of this document are confidential and proprietary to Quintiles Transnational Corp. Unauthorized use, disclosure or reproduction is strictly prohibited.

- Negative at Month 24:
  - o Participants who are negative at Month 24 or who initially converted at Month 6 or Month 12 and are negative at the  $\geq 24$  Month call-back visit.
- Prevention of conversion OR conversion with reversion:
  - o Participants who are consistently negative OR
  - o Participants who have a negative QFT-GIT value within six months after their initial conversion (i.e., +/-/-, +/+/-, +/-/+, +/m/-, +/-/m).
- Prevention of conversion OR conversion with reversion and non-positive (i.e. negative or missing) QFT-GIT results at six-months post-initial-conversion:
  - o Participants who are consistently negative OR
  - o Participants who have a negative QFT-GIT value at the last available testing timepoint within six months after their initial conversion (i.e., +/-/-, +/+/-, +/m/-, +/-/m).
- Prevention of conversion OR conversion with reversion and non-positive (i.e., negative or missing) QFT-GIT results at the end of the study:
  - o Participants who are consistently negative throughout the study OR
  - o Participants who initially converted at Month 18 or Month 24 (i.e., +/-/-, +/+/-, +/m/-, +/-/m) and later reverted OR
  - o Participants who initially converted at Month 6 or Month 12 and have a call-back Month 24 visit that is negative (i.e., +/-/-/-, +/+/-/-, +/+/+/-, +/-/+/-, +/-/m/-, +/m/-/-, +/m/m/-, +/+/m/-).
- QFT-GIT end of study sustained conversion status:
  - o Yes: At 3 and 6 months following first QFT-GIT conversion AND at the Month 24 call-back visit (if applicable), QFT-GIT result classifications are derived as positive.
  - o No: At 3 and/or 6 months following first QFT-GIT conversion and/or at the Month 24 call-back visit (if applicable), QFT-GIT result classification is derived as negative.
  - o Missing: None of the aforementioned QFT-GIT result classifications (yes, no) has been assigned at 3 or 6 months post-conversion or at the Month 24 call-back visit, QFT-GIT result classification is derived as missing.
- The confidence interval for VE is calculated using the conditional binomial method (Clopper-Pearson method with mid-p correction) as follows:  
 The number of participants with a conversion ( $n_A$ ) in one of the treatment groups (for example H4:IC31) and the number ( $n_B$ ) of participants with a conversion in another treatment group (for example Placebo), are assumed to have Independent Poisson distributions with rate parameters  $\lambda_A$  and  $\lambda_B$ , respectively, but inference is conditional on the total number of conversions,  $n = n_A + n_B$ . Conditional on  $n$ ,  $n_A$  has a Binomial distribution,  $\text{Bin}(n, \pi)$ , where

$$\pi = \frac{\lambda_A F_A}{\lambda_A F_A + \lambda_B F_B} = \frac{\theta F_A}{\theta F_A + F_B}$$

$\theta = \lambda_A \lambda_B$  and  $F_A$  and  $F_B$  are the total lengths of follow-up across all subjects in the relevant treatment groups (Treatment Group A/Treatment Group B), that is,  $F = \sum (\text{Duration of VE Follow-up Period [Days]})$ .

Document: Aeras\_C-040-404\_SAP\_V2\_0

Author: [name]

Version Number:

2.0

Version Date:

29SEP2017

Template No: CS\_TP\_BS016 – Revision 3

Reference: CS\_WI\_BS005

Effective Date: 01May2012

Copyright © 2012 Quintiles Transnational Corp. All rights reserved.

The contents of this document are confidential and proprietary to Quintiles Transnational Corp. Unauthorized use, disclosure or reproduction is strictly prohibited.

A point estimate and exact two-sides 95% CI ( $\pi_L, \pi_U$ ) for  $\pi$  is then calculated (Clopper - Pearson method with mid-p correction) based on the number of participants with a conversion in one of the treatment groups (for example H4:IC31), relative to the total number of participants  $n = n_A + n_B$  who had at a conversion in either of the two compared treatment groups. The following SAS® code will be used:

```
PROC FREQ DATA = <>;
    TABLE Events / BINOMIAL (midp P=0.05);
RUN;
```

Based on the exact 95% CI for  $\pi$ , an exact 95% CI ( $\theta_L, \theta_U$ ), for the rate ratio  $\theta$  is then calculated by solving the equations:

$$\frac{\theta_L F_A}{\theta_L F_A + F_B} = \pi_L$$

$$\frac{\theta_U F_A}{\theta_U F_A + F_B} = \pi_U$$

Solving  $\theta_L$  and  $\theta_U$  yields:

$$\theta_L = \left( \frac{\pi_L}{1 - \pi_L} \right) \left( \frac{F_B}{F_A} \right)$$

$$\theta_U = \left( \frac{\pi_U}{1 - \pi_U} \right) \left( \frac{F_B}{F_A} \right)$$

Finally, the exact 95% CI ( $VE_L, VE_U$ ) for VE is calculated as

$$VE_L = (1 - \theta_U)$$

$$VE_U = (1 - \theta_L)$$

In summary, the VE point estimate and confidence limits for the aforementioned binomial proportion ( $\pi$ ) will be substituted in the following formula in order to obtain the corresponding confidence limits for the VE:

$$VE = \left( \frac{(\pi) F_B}{(1 - \pi) F_A} \right)$$

Document: Aeras\_C-040-404\_SAP\_V2\_0

Author: [name]

Version Number:

2.0

Version Date:

29SEP2017

Template No: CS\_TP\_BS016 – Revision 3

Reference: CS\_WI\_BS005

Effective Date: 01May2012

Copyright © 2012 Quintiles Transnational Corp. All rights reserved.

The contents of this document are confidential and proprietary to Quintiles Transnational Corp. Unauthorized use, disclosure or reproduction is strictly prohibited.

Where the lower confidence limit for VE is obtained by substituting the upper confidence limit for  $\pi$  in the above formulae, and the upper confidence limit for VE is obtained by substituting the lower confidence limit for  $\pi$  in the above formula.

- Bacteriologically confirmed TB:
  - o Positive culture result (Mycobacterium tuberculosis positive)  
OR
  - o Positive GeneXpert result (MTB detected) (with or without clinical symptoms and/or positive chest x-ray).

---

Document: Aeras\_C-040-404\_SAP\_V2\_0

Author: [name]

Version Number:

2.0

Version Date:

29SEP2017

Template No: CS\_TP\_BS016 – Revision 3

Reference: CS\_WI\_BS005

Effective Date: 01May2012

Copyright © 2012 Quintiles Transnational Corp. All rights reserved.

The contents of this document are confidential and proprietary to Quintiles Transnational Corp. Unauthorized use, disclosure or reproduction is strictly prohibited.

